6.3.1.2 Alpelisib/placebo

Management of severe or intolerable adverse reactions requires dose reduction, temporary interruption, and/or discontinuation of alpelisib therapy. A maximum of 2 dose reductions will be allowed, after which the patient will be discontinued from treatment with alpelisib/placebo. Dose reduction should be based on the worst preceding toxicity.

Please refer to [Table 6-2](#) and [Table 6-3](#) for guidance.

Table 6-2 Dose reduction sequential steps for alpelisib/placebo

Alpelisib/placebo dose level	Dose and schedule	Number of tablets & strength
Starting dose	300 mg/day continuously	1 x 200 mg tablet and 2 x 50 mg tablet
Dose level -1	250 mg/day continuously	1 x 200 mg tablet and 1 x 50 mg tablet
Dose level -2	200 mg/day continuously	1 x 200 mg tablet

Recommendations for dose reduction or dose interruption of alpelisib/placebo in the management of adverse reactions are summarized in [Table 6-3](#). No dose modification for fulvestrant is permitted. Clinical judgment of the treating physician, including confirmation of lab values if deemed necessary, should guide the management plan of each patient based on individual benefit/risk assessment.

However, treatment must be discontinued as indicated in [Table 6-3](#).

After treatment is resumed at a lower dose:

- If the same toxicity recurs with the same severity, then the next treatment re-initiation must resume at a lower dose irrespective of duration.
- Once the alpelisib/placebo dose has been reduced, no re-escalation will occur, even upon resolution of AE.

If a patient requires a dose delay of alpelisib/placebo for > 28 days from the intended day then the patient must be discontinued from alpelisib/placebo, but may continue on fulvestrant. All scheduled assessments will continue to be performed. If fulvestrant is held for more than 35 days since a planned injection, then fulvestrant should be permanently discontinued. The patient may continue on alpelisib/placebo at the discretion of the investigator until study completion, in which case all scheduled assessments will continue to be performed.

Table 6-3 Criteria for interruption and re-initiation of alpelisib/placebo treatment

Dose Modifications for alpelisib/placebo as specified below. Fulvestrant may be continued while alpelisib/placebo dose is being held, at the investigators discretion, and as specified in Section 6.3.1	
Worst toxicity -CTCAE Grade (value)	Dose Modifications for alpelisib/placebo

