Grade 4 (FPG > 500 mg/dL) [≥ 27.8 mmol/L]	
Omit alpelisib/placebo, confirm fasting status of the assessment. If non-fasting, re-check within 24 hours.
 
 • Regardless of fasting status, consider IV fluids. Exclude confounding factors like e.g. urinary tract infection. • Should consult with diabetologist, initiate or intensify medication with appropriate anti-diabetic treatment (see Grade 3), re-check within 24 hours. • If grade improves then follow specific grade recommendations • If FPG is confirmed at Grade 4 and confounding factors could be excluded, permanently discontinue patient from alpelisib/placebo.

Dose Modifications for alpelisib/placebo as specified below. Fulvestrant may be continued while alpelisib/placebo dose is being held, at the investigators discretion, and as specified in Section 6.3.1	
Worst toxicity -CTCAE Grade (value)	Dose Modifications for alpelisib/placebo
A diabetologist consultation should always be considered. For all grades : instruct patient to follow dietary guidelines according to local and/or institutional standards for management of diabetes mellitus (such as those provided by the American Diabetes Association) during the study, e.g. controlled carbohydrate intake, high fiber, low processed food intake; three macronutrient balanced meals and 2 small snacks rather than one large meal.	
* specific recommendations please see Section 6.3.2.1.3 .	
Thrombocytopenia	
Grade 1 (PLT < LLN - $75 \times 10^9/L$)	Maintain dose level
Grade 2 (PLT < $75 - 50 \times 10^9/L$)	
Grade 3 (PLT < $50-25 \times 10^9/L$)	Omit dose until resolved to \leq Grade 1, then: 
 • If resolved in \leq 7 days, then maintain dose level • If resolved in $>$ 7 days, then \downarrow 1 dose level
Grade 4 (PLT < $25 \times 10^9/L$)	Omit dose until resolved to \leq Grade 1, then \downarrow 1 dose level
Investigations (Renal)	
Serum creatinine	
< 2 x ULN	Maintain dose level
2 – 3 x ULN	Omit dose until resolved to \leq grade 1, then: 
 • If resolved in \leq 7 days, then maintain dose level • If resolved in $>$ 7 days, then \downarrow 1 dose level
Grade 3 (> 3.0 – 6.0 x ULN)	Permanently discontinue patient from alpelisib/placebo
Grade 4 (> 6.0 x ULN)	Permanently discontinue patient from alpelisib/placebo
Investigations (Hepatic)	
Isolated total Bilirubin elevation	

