* Note: If total bilirubin > 3.0 x ULN is due to the indirect (non-conjugated) component only, and hemolysis as the etiology has been ruled out as per institutional guidelines (e.g. review of peripheral blood smear and haptoglobin determination), then ↓ 1 dose level and continue treatment at the discretion of the investigator.	

Dose Modifications for alpelisib/placebo as specified below. Fulvestrant may be continued while alpelisib/placebo dose is being held, at the investigators discretion, and as specified in Section 6.3.1	
Worst toxicity -CTCAE Grade (value)	Dose Modifications for alpelisib/placebo
Investigations (Cardiac)	
Cardiac – QTc prolongation	
QTcF > 500 ms (\geq Grade 3) or > 60 ms change from baseline on at least two separate ECGs	
First Occurrence:
 
 1. Assess the quality of the ECG recording and the QT value and repeat if needed 2. Interrupt study treatment 3. Determine the serum electrolyte levels (in particular hypokalemia, hypomagnesemia). If abnormal, correct abnormalities before resuming study drug treatment. 4. Review concomitant medication use for other causes for QT prolongation (refer to crediblemeds.org for known QT prolonging drugs), and for drugs with the potential to increase the risk of drug exposure related QT prolongation 5. Check study drug dosing schedule and treatment compliance 6. Consider collecting a time-matched PK sample and record time and date of last study drug intake. 
After confirming ECG reading at site, if QTcF > 500 ms or > 60 ms change from baseline
 
 • Interrupt study treatment • Repeat ECG and confirm ECG diagnosis by a cardiologist 
If QTcF confirmed > 500 ms or > 60 ms change from baseline
 
 • Correct electrolytes, eliminate culprit concomitant treatments, and identify clinical conditions that could potentially prolong the QT • Consult with a cardiologist (or qualified specialist) • Increase cardiac monitoring as indicated, until the QTcF returns to \leq 480 ms or < 60ms change from baseline. • After resolution to \leq 480 ms /60 ms change from baseline, consider re-introducing treatment at reduced dose, and increase ECG monitoring • If QTcF remains \leq 500 ms/60 ms change from baseline after dose reduction, continue planned ECG monitoring during subsequent treatment • If QTcF recurs > 500 ms/60 ms change from baseline after dose reduction, discontinue patient from alpelisib/placebo.

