Any Grade of Stevens-Johnson-Syndrome /Toxic Epidermal Necrolysis/Drug Reaction with Eosinophilia and Systemic Symptoms (DRESS) or other SJS/TEN/DRESS like severe skin reactions	
Permanently discontinue patient from alpelisib/placebo
 
Consult a dermatologist, ensure documentation by imaging like photographs, and obtain a skin biopsy
 
Follow local treatment guidelines for SJS/TEN/ DRESS

**Active" skin toxicities: If there are no new lesions or new areas of involvement developing, and if lesion appearance is changing color from red to pale or light brown, it is likely the skin toxicity has begun to fade and is not to be considered "active" any longer. Treatment reduction can be considered for these areas. The appearance of skin toxicity may fade slowly, over 10 days or more but not requiring ongoing therapy.	
Immune system disorders	
Hypersensitivity	
Please see specific instructions in Section 6.3.2.1.6	
Investigations (Pulmonary disorders)	
Pneumonitis	
Please see specific instructions in Section 6.3.2.1.1 .	
Investigations (Metabolic)	
Asymptomatic amylase and/or lipase elevation (see also Section 6.3.2.1.4)	
Grade 1 (> ULN - 1.5 x ULN)	Maintain dose level
Grade 2 (> 1.5 - 2.0 x ULN)	Maintain dose level
Grade \geq 3 (> 2.0 x ULN)	
Omit dose until resolved to baseline, then
 
 • If resolved in \leq 14 days, maintain dose level • If resolved in $>$ 14 days, then \downarrow 1 dose level. 
Note:
 
 • In cases of isolated amylase elevations only, dosing may be maintained provided amylase fractionation demonstrates that pancreatic amylase is \leq Grade 1. Monitor total amylase (and continue to assess fractionated amylase) as specified in Section 6.3.2.1.4.
Note: Withhold study treatment for acute onset of new or progressive unexplained abdominal symptoms, such as severe pain or vomiting; and perform diagnostic procedures (e.g. abdominal CT scan or ultrasound) to exclude pancreatic pathology.	
Investigations (any other)	
Other adverse events	
Grade 1 or 2	Maintain dose level
Grade 3	Omit dose until resolved to \leq grade 1, then \downarrow 1 dose level
Grade 4	
Permanently discontinue from alpelisib/placebo
 
Omit dose for \geq grade 3 vomiting or grade 3 nausea only if the vomiting or nausea cannot be controlled with optimal antiemetic (as per local practice)

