8.1 Adverse events

8.1.1 Definitions and reporting

An adverse event is defined as the appearance of (or worsening of any pre-existing) undesirable sign(s), symptom(s), or medical condition(s) that occur after patient's signed informed consent has been obtained.

Abnormal laboratory values or test results occurring after informed consent constitute adverse events only if they induce clinical signs or symptoms, are considered clinically significant, require therapy (e.g. hematologic abnormality that requires transfusion or hematological stem cell support), or require changes in study medication(s).

Adverse events that begin or worsen after informed consent should be recorded in the adverse events CRF. Conditions that were already present at the time of informed consent should be recorded in the Medical History page of the patient's CRF. Adverse event monitoring should be continued for at least 30 days following the last dose of study treatment. Adverse events (including lab abnormalities that constitute AEs) should be described using a diagnosis whenever possible, rather than individual underlying signs and symptoms. When a clear diagnosis cannot be identified, each sign or symptom should be reported as a separate Adverse Event.

Adverse events will be assessed according to the Common Terminology Criteria for Adverse Events (CTCAE) version 4.03.

If CTCAE grading does not exist for an adverse event, the severity of mild, moderate, severe, and life-threatening, corresponding to Grades 1 - 4, will be used. CTCAE Grade 5 (death) will not be used in this study; rather, information about deaths will be collected through a Death form.

The occurrence of adverse events should be sought by non-directive questioning of the patient (subject) during the screening process after signing informed consent and at each visit during the study. Adverse events also may be detected when they are volunteered by the patient (subject) during the screening process or between visits, or through physical examination, laboratory test, or other assessments. As far as possible, each adverse event should be evaluated to determine:

1. The severity grade (CTCAE Grade 1-4)
2. Its duration (Start and end dates)
3. Its relationship to the study treatment (Reasonable possibility that adverse event is related: No, Yes)
4. Action taken with respect to study or investigational treatment (none, dose adjusted, temporarily interrupted, permanently discontinued, unknown, not applicable)

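### Table 6-3 gives Grade 4 vomiting two incompatible instructions: stop alpelisib/placebo permanently, or omit the dose only if antiemetics fail

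*Protocol*

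**What the plan says.** Protocol Section 6.3.1.2 sets the dose rules for alpelisib/placebo in Table 6-3. In the last block, for adverse events not listed elsewhere:

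- Grades 1 and 2: keep the dose.
- Grade 3: omit until Grade 1 or better, then go down one dose level.
- Grade 4: "Permanently discontinue from alpelisib/placebo".
- The next line, which opens with an instruction to omit the dose and a ≥ sign: "grade 3 vomiting or grade 3 nausea only if the vomiting or nausea cannot be controlled with optimal antiemetic (as per local practice".

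The text above the table treats reductions and interruptions as recommendations guided by clinical judgment, then adds: "However, treatment must be discontinued as indicated in" Table 6-3.

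Section 8.1.1 fixes the grading scale: "The severity grade (CTCAE Grade 1-4", and "CTCAE Grade 5 (death) will not be used in this study".

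**The concern.** A severe event should carry one instruction. Section 8.1.1 equates Grade 4 with life-threatening severity where CTCAE has no grading of its own. A site facing Grade 4 vomiting could stop the drug for good under one line. Under the other it could hold the drug, or continue if antiemetics work. The vomiting line also gives no restart rule: the resume-at-one-level-lower rule stands only in the Grade 3 row. A site that holds the drug at Grade 4 is not told when, or at what dose, to resume.

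There is a small reporting consequence. SAP Section 3.9.1.4 tabulates events leading to discontinuation separately from events requiring adjustment or interruption, so the same event could be counted in either table depending on which line the site followed.

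**Working it through.** The plan states no figure to reproduce here. The check sets the texts side by side and then bounds the frequency.

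**Step 1: which grades overlap.** Grades in use are {1, 2, 3, 4} (Section 8.1.1). At or above Grade 3 therefore means {3, 4}. The permanent-stop row covers {4}. The overlap is {4}: one grade. The ≥ sign stands before vomiting only; nausea is named at Grade 3 alone.

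**Step 2: what each line requires.**

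| Case | Graded rows | Vomiting line |
|---|---|---|
| Grade 4, controlled by antiemetics | Permanent stop | No omission |
| Grade 4, not controlled | Permanent stop | Omit the dose |
| Grade 3 vomiting or nausea | Omit, then one level lower | Omit only if antiemetics fail |

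The instructions differ in both Grade 4 cases. At Grade 3 there is no conflict, because the line simply qualifies the rule to omit.

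**Step 3: does another text settle it?**

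- Section 6.3.1.2 makes discontinuation as indicated in the table mandatory. The vomiting line indicates no discontinuation; it says only when to omit. The one discontinuation indicated for this category is the Grade 4 row, so this favours the permanent stop.
- Table 6-3 also stops treatment at Grade 4, without condition, for diarrhea and stomatitis. That points the same way.
- Against this, Table 6-3 holds rather than stops at Grade 4 for thrombocytopenia (omit, then one level lower) and for asymptomatic amylase or lipase elevation at Grade 3 or above (omit, then the same or one lower level). Holding at Grade 4 is therefore not foreign to the table.
- Where a Grade 4 stop is made conditional, the condition is tied to its row. Hyperglycemia: "If FPG is confirmed at Grade 4 and confounding factors could be excluded, permanently discontinue patient from alpelisib/placebo". Bilirubin has an asterisked note for a rise above 3 times the upper limit of normal that "is due to the indirect (non-conjugated) component only, and hemolysis as the etiology has been ruled out as per institutional guidelines". The vomiting line is not marked as an exception to the Grade 4 row.
- The note on abdominal symptoms ("Withhold study treatment for acute onset of new or progressive unexplained abdominal symptoms, such as severe pain or vomiting") withholds treatment pending a pancreatic work-up. It does not say whether Grade 4 vomiting is a permanent stop.

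**Step 4: how often.** Table 1-2 (phase I combination with fulvestrant, treatment-related vomiting, Grades 3 and 4 pooled) gives 0/9 at 300 mg, 0/8 at 350 mg, 1/66 at 400 mg and 1/84 overall. Grade 4 alone was therefore 0/84 = 0% or 1/84 = 1.2%, and 0/9 at the trial's starting dose. These counts are not projected to this trial; neither the number of Grade 4 cases nor the number of patients still on treatment is given.

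**The case against.** The strongest reply is that the plan already has a hierarchy. Omission is a recommendation and discontinuation is mandatory, so the Grade 4 row governs and the ≥ sign is surplus. Most of this stands: a careful reader of Section 6.3.1.2 should arrive at the permanent stop. But that takes inference, because the conflicting line stays in the table and nothing says that it yields.

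A second reply runs the other way. The specific line overrides the general row; the ≥ sign was put on vomiting and not on nausea, which looks like a choice; and the table does hold at Grade 4 for two other toxicities. This cannot be excluded, and it is why the fix must leave the sponsor an explicit alternative. It does not make the present text clear, since the line is not labelled an exception and carries no restart dose.

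A third reply is that extraction from PDF may have merged a separate note into the Grade 4 cell. That would not matter. The overlap comes from the ≥ sign, wherever the line sits.

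Safeguards also limit the harm. A life-threatening event is serious (Section 8.2.1) and is reported within 24 hours (Section 8.2.2). A hold of more than 28 days forces discontinuation of alpelisib/placebo (Sections 6.3.1.2 and 7.1.3). The investigator should stop if continuing would be detrimental (Section 7.1.3).

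**Conclusion.** The conflict is real, confined to one grade of one event, and minor. The two lines cannot both be followed for Grade 4 vomiting. Section 6.3.1.2 and the diarrhea and stomatitis rows favour the permanent stop without removing the contrary line. The expected frequency is low on the only data given (at most 1 of 84; 0 of 9 at 300 mg), and no efficacy, alpha or power figure depends on it.

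A reader might infer more than the documents support:

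- That the protocol gives no guide at all. It does, through the mandatory discontinuation sentence.
- That the ≥ sign is plainly a slip, or plainly an intended exception. The documents do not show which.
- That patients were kept on drug after Grade 4 vomiting. Nothing in the plan shows that any such case occurred.

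The conclusion rests on the ≥ sign being correctly reproduced in the text; nothing suggests that it is misread.

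**What to change.** In Table 6-3, limit the line to Grade 3 vomiting and Grade 3 nausea by removing the ≥ sign, and move it to the Grade 3 row. The permanent stop then applies to Grade 4 vomiting, which is the safer reading and the one that Section 6.3.1.2 favours. If the sponsor intends a Grade 4 exception, state it in the Grade 4 row, with the condition and the dose at which treatment resumes.

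The edit is one symbol and a move, or one explicit sentence. Under Section 12.1 it still needs a written amendment approved by the sponsor, by health authorities where required, and by the ethics committees. It can travel with the next amendment. Sites with patients still on treatment should receive a short notice. No analysis changes.

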6.3.2 Follow-up for toxicities

All patients must be followed up for safety (adverse events and serious adverse events) for 30 days following the last dose of study treatment (alpelisib/placebo and/or fulvestrant). Patients whose treatment is interrupted or permanently discontinued due to an adverse event, including abnormal laboratory value, must be followed until resolution or stabilization of the event, whichever comes first which includes all study assessments appropriate to monitor the event. Further guidelines and recommendations for the management of specific study treatment combination-induced toxicities are provided below.

6.3.2.1 Additional follow-up for selected toxicities

6.3.2.1.1 Management of pneumonitis /Interstitial lung disease

Alpelisib is associated with pneumonitis/interstitial lung disease. Closely monitor all patients for signs and symptoms of pneumonitis.

All patients will be routinely asked about and observed for the occurrence of adverse events including new or changed pulmonary symptoms (consistent with lung abnormalities). Patients who are suspected to have developed pneumonitis should suspend (alpelisib/placebo) immediately (but may continue fulvestrant if clinically indicated) and undergo appropriate imaging (high resolution CT scan) and broncho-alveolar lavage (BAL) and biopsy should be considered if clinically appropriate. Infectious causes of interstitial lung disease should be ruled out. Infectious causes of interstitial lung disease should be ruled out. Investigators should follow institutional practice for management of pneumonitis which generally includes treatment with high dose corticosteroids; antibiotic therapy should be administered concurrently if infectious causes are suspected. Consultation with a pulmonologist is highly recommended for any pneumonitis case during the study treatment. After ruling out infectious etiology and upon making a diagnosis of pneumonitis, permanently discontinue treatment with alpelisib/placebo and promptly initiate appropriate treatment and supportive measures.

~~Alpelisib/placebo should be permanently discontinued in all subjects with confirmed pneumonitis.~~

6.3.2.1.2 Guidelines for the treatment of study drug induced skin toxicity

Skin toxicity is a class-effect adverse event observed with PI3Ki/mTORi agents.

Close monitoring of potential skin reactions will be performed at each planned visit and will be reported as adverse event. The most frequent skin adverse events reported are: maculopapular rash (only a minority present acneiform rash); pruritus and dry skin. The onset is typically within the first 2 months of treatment start and is reversible with adequate comedication and treatment interruption if needed. Skin reactions may improve over several weeks. Consultation with a dermatologist is highly recommended for better assessment and management of alpelisib-induced skin toxicity at any grade, and mandated if severe cutaneous reaction like

Stevens-Johnson-Syndrome, Toxic Epidermal Necrolysis or Erythema multiforme or Drug Reaction with Eosinophilia and Systemic Symptoms (DRESS) is suspected. Workup for skin toxicity events includes skin photography, a complete blood count with differential, and a full chemistry panel. A paired skin biopsy should be obtained (from both affected and an unaffected skin area) for local histopathology assessment to further assess the skin toxicity, especially to confirm suspected diagnosis of any severe cutaneous reactions.

Skin photographs must be taken and skin biopsy must be performed in case of Grade 4 skin toxicity and any grade of suspected severe cutaneous reactions. In case of Grade 3 skin toxicity, Novartis recommends that photographs are taken and a skin biopsy is performed.

Skin biopsy will be sent to a Novartis designated laboratory, together with dermatologist and pathologist reports, if available, for further research purpose on the pathology and mechanism of PI3K inhibitor treatment induced skin toxicity

Antihistamines administered prior to rash onset may decrease incidence and severity of rash based on Study CBYL719C2301; therefore, at the Investigator's discretion, non-sedating antihistamines (e.g. cetirizine (Zyrtec[®]), fexofenadine (Allegra), loratadine (Claritin)) may be used as prophylactic treatment to reduce severity of rash in all patients and especially for patients with a history of atopy such as allergic rhinitis, asthma, atopic dermatitis, or drug allergies.

For any grade of severe cutaneous reactions, alpelisib treatment must be permanently discontinued without any re-challenge.

Recommended therapies for skin toxicity events of all grades and as clinically indicated include:

- Mid to high potency topical steroids: triamcinolone 0.01% or fluocinonide 0.05% twice daily for at least 28 days. Recommend spray, lotion, or cream preparation for ease of application on trunk. For scalp involvement, recommend a foam or solution preparation.
- Gamma-aminobutyric acid (GABA) Agonists: Gabapentin 300mg every 8 hours, Pregabalin 50-75 mg every 8 hours (to adjust of renal impairment). Depending on patient's clinical condition be aware of potential and common side effects observed with GABA agonists such as: somnolence, dizziness (both drugs) and peripheral edema (Gabapentin) among others adverse events. For grade 4 skin events or any grade of severe cutaneous reactions (including SJS, TEN, EM, DRESS), alpelisib treatment must be permanently discontinued without any re-challenge.

Dry skin has been reported. It is recommended that patients with dry skin use mild and fragrance free soaps and detergents.

Although preclinical experiments demonstrated that patients should avoid sun exposure during treatment with ~~buparlisib~~ or alpelisib, especially when they already have experienced rash or other skin toxicities as the increased blood flow of the skin may worsen skin symptoms. Patients should be advised to take measures to protect themselves from direct exposure to sunlight, including the wearing of sunglasses as well as the regular use of sunscreen, hats, long-sleeve shirts and long pants when outdoors.

